1.3 Benefit-risk assessment

Healthy subjects in this study will not receive any direct health-related benefit from administration of levodopa, carbidopa and ODM-104. However, the study subjects will receive general information on their current health by laboratory tests, electrocardiograms (ECGs), physical examination including blood pressure (BP) and heart rate (HR) measurements.

Levodopa, carbidopa and ODM-104 have been generally well tolerated and safe in previous PK studies (studies 3112001, 3112002 and 3112003) and in an ongoing study (3112004) in patients with PD; however, they are known to cause different symptoms in some subjects. Headache, nausea, nasopharyngitis, flatulence, vomiting, increased blood creatine phosphokinase, constipation and dizziness were reported relatively frequently in previous PK studies with ODM-104. In addition, isolated cases of cardiac conduction abnormalities and mild increases in liver transaminases were reported. No serious adverse events (SAEs) have been reported in previous phase I studies on ODM-104. Based on these findings as well as the nonclinical data on ODM-104, the events of increase in liver tests, cardiac arrhythmias and gastrointestinal irritation are considered as important potential risks for ODM-104. These risks are subject to close monitoring during the clinical program.

Carbidopa single dose used in the test treatments is higher than those in many levodopa treatments on the market with 4 to 1 levodopa to carbidopa ratio. However, the dosing frequency is 4 times a day and the total daily dose of carbidopa will not exceed the daily dose of the approved levodopa products in this study. Higher carbidopa dose has been used in combination with levodopa and ODM-104 in the previous PK studies and in the ongoing study in patients. In the present study subjects remain in the research institute for the whole duration of the dosing period. Samples for laboratory tests and ECG monitoring are applied to exclude subjects with abnormalities from entering the study and after treatment initiation to be discontinued if specified abnormalities emerge. Signs of nausea, gastrointestinal and other symptoms will be followed clinically daily and if intolerable, treatment will be discontinued.

Blood sampling may cause local pain and haematoma as well as fainting in isolated cases. In addition, ECG electrodes attached to the skin may cause irritation.

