4.3 Exclusion criteria

Subjects will not be included into this study if they meet any of the following criteria:

1. Evidence of clinically significant cardiovascular, renal, hepatic, haematological, gastrointestinal, pulmonary, metabolic, endocrine, neurological or psychiatric disease or cancer (except local non-melanoma skin cancer) within the previous 2 years.
2. Any condition requiring regular concomitant treatment (including vitamins and herbal products) or likely to need any concomitant treatment during the study. As an exception, paracetamol for occasional pain is allowed.
3. Any clinically significant abnormal laboratory value or ECG (such as prolonged QTcF >450 ms or QRS >120 ms) that in the opinion of the investigator could interfere with the interpretation of study results or cause a health risk for the subject if he takes part in the study.
4. Known hypersensitivity to the active substances or the excipients of the drugs.
5. History of vasovagal collapses or vagal reactions with unexplained reason within the previous 2 years or a tendency for vasovagal reactions during blood sampling.
6. HR < 50 bpm or > 90 bpm in the supine position after 5 min rest at the screening visit.
7. At the screening visit:
 - systolic BP < 100 mmHg or > 140 mmHg in the supine position after 5 min rest
 - diastolic BP < 50 mmHg or > 90 mmHg in the supine position after 5 min rest.
8. Creatinine > 1.5 x upper limit of normal (ULN) and alanine aminotransferase or aspartate aminotransferase >1.25 x ULN at screening.
9. History of anaphylactic/anaphylactoid reactions.
10. Strong tendency to motion sickness.
11. Recent or current (suspected) drug abuse.
12. Recent or current alcohol abuse; regular drinking of more than 21 units per week (1 unit = 4 cl spirits or equivalent).
13. Current use of nicotine-containing products more than 5 cigarettes (or equivalent)/day and/or inability to refrain from the use of nicotine-containing products for 48 h before

the first dose in each period until collection of the 24 h PK sample in the morning of day 8.

14. Use of caffeine-containing beverages more than 600 mg of caffeine/day and/or inability to refrain from using caffeine-containing beverages 24 h before the first levodopa administration on the PK day (day 7) until collection of the 24 h PK sample in the morning of day 8.
15. Blood donation or loss of a significant amount of blood (> 500 ml) within 90 days before the first study treatment administration.

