4.5 Removal of subjects from treatment or assessment

Study subjects are free to discontinue the study at any time without providing a reason. However, the investigator should try to identify the reason and document it on the eCRF.

A subject must discontinue the study treatment if the investigator or the sponsor considers the discontinuation to be medically necessary or in the best interest of the subject.

A subject must discontinue the study treatment for example for the following reasons:

- Personal reason
- AE requiring discontinuation of the study treatment, as judged by the investigator:
 - Intolerable dopaminergic AEs such as prolonged moderate or severe vomiting with massive fluid loss and consequent circulatory disorders
 - Intolerable gastrointestinal AEs such as prolonged moderate or severe diarrhoea with massive fluid loss and consequent circulatory disorders
 - Abnormal 12-lead ECG finding of clinical relevance:
 - increase in QTc of >60 ms from baseline
 - increase in QRS of >25% from baseline

- 2nd or 3rd degree atrioventricular block
- sustained (>30 s) cardiac arrhythmias (supraventricular or ventricular tachycardia, atrial fibrillation and/or flutter)
- any symptomatic arrhythmia (except isolated extrasystoles)
- Increase in alanine aminotransferase, aspartate aminotransferase or alkaline phosphatase to >3 x ULN
- Other AE (e.g. fainting or profound weakness) requiring discontinuation of the study treatment
- Lost to follow-up
- Protocol deviation that could affect the outcome of the study, as judged by the investigator
- Other reason (e.g. impossibility to obtain blood samples)

Irrespective of the reason for discontinuation, the subject should be invited to end-of-study assessments as soon as possible. As long as the subject consents, all relevant assessments, at least those of safety, should be performed, preferably according to the schedule for the end-of-study assessments.

The study monitor should be notified about premature discontinuations within 24 h in the event of discontinuation due to an SAE (see section 6.4.1.3) or within 7 days in the event of discontinuation due to another reason.

The sponsor will decide if study subjects who prematurely discontinue will be replaced. Discontinued study subjects are not allowed to re-enter the study.

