6.1.1 Procedures during the screening period

Screening procedures will start after receiving approval from the ethics committee (EC) and competent authority (CA).

A prospective subject will receive both written and verbal information about the study and will have an opportunity to ask questions and sufficient time to decide whether or not to participate in the study. A signed and dated written IC for the main study will be obtained prior to any screening activities (see section 11.3). A separate pharmacogenomic (PG) IC will be obtained from subjects who agree to take part in the optional study-related exploratory PG study (see section 6.3).

The screening visit will take place within 21 days before the first study treatment administration.

The following procedures will be performed at the screening visit:

- Physical examination will be performed.
- Demographic data (sex, year of birth, age and racial group), substance use (use of nicotine, alcohol and caffeine, and drug abuse) and weight, height and BMI will be recorded.
- Medical history, current medical conditions and concomitant treatments will be recorded.
- AEs will be recorded.
- BP and HR will be recorded in the supine position after at least 5 min rest.
- 12-lead ECG will be recorded in the supine position after at least 5 min rest.
- Alcohol breath testing will be performed.
- Blood samples for haematology, clinical chemistry and serology will be collected after fasting for at least 10 h; see section 6.4.5 for details.
- Urine drug abuse testing will be performed.
- Urinalysis will be performed.
- Columbia-Suicide Severity Rating Scale (C-SSRS) will be performed.
- Subjects will be instructed to call the study centre when they experience AE or need to take concomitant treatment after the screening visit until the end-of-study visit when they are not in-house.

For practical reasons, the procedures outlined above may be performed on 2 separate occasions, for example, the physical examination may be performed a couple of days later than the other procedures.

A subject will be entered into the study if all of the inclusion criteria and none of the exclusion criteria are met and will be randomised to one of the treatment sequences before starting study treatments.

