6.4.5 Laboratory safety assessments

The following laboratory tests will be taken at the screening visit after at least 10 h of fasting:

Haematology:

- Haemoglobin
- Haematocrit
- Erythrocytes
- Thrombocytes
- Mean corpuscular volume
- Mean corpuscular haemoglobin
- Mean corpuscular haemoglobin concentration
- Leucocytes
- Differential count (lymphocytes, monocytes, eosinophils, neutrophils, basophils)

Clinical chemistry:

- Albumin
- Creatinine
- Alkaline phosphatase
- Alanine aminotransferase

- Aspartate aminotransferase
- Creatine kinase
- Gamma-glutamyl transferase
- Glucose
- Magnesium
- Sodium
- Potassium
- Calcium (albumin corrected)
- C-reactive protein
- Thyroid stimulating hormone
- Total bilirubin

Urinalysis:

- Stick-test: pH, leucocytes¹, nitrites¹, protein, blood¹, glucose (¹ in case of findings, a microscopy examination of urine sediment will be performed)

Serology:

- Human immunodeficiency virus antigen/antibody
- Hepatitis C virus antibodies
- Hepatitis B-surface antigen

Selected laboratory tests

The following selected laboratory tests will be performed on days 1 and 7 in each treatment period, before the first dose:

Haematology:

- Haemoglobin
- Haematocrit
- Erythrocytes
- Thrombocytes
- Mean corpuscular volume
- Mean corpuscular haemoglobin
- Mean corpuscular haemoglobin concentration
- Leucocytes

- Differential count (lymphocytes, monocytes, eosinophils, neutrophils, basophils)

Clinical chemistry:

- Creatine kinase
- Creatinine
- Alkaline phosphatase
- Aspartate aminotransferase
- Gamma-glutamyl transpeptidase
- Alanine aminotransferase
- Total bilirubin
- Sodium
- Potassium
- Magnesium
- C-reactive protein

Urinalysis

- Stick-test: pH, leucocytes¹, nitrites¹, protein, blood¹, glucose (¹in case of findings, a microscopy examination of urine sediment will be performed)

End-of-study laboratory tests

The same laboratory tests as at the screening visit, except determination of thyroid stimulating hormone and albumin, serology tests, urine test for drug abuse and alcohol breath test will be performed.

Alcohol and drug abuse tests during the study

An alcohol breath test will be performed at the screening visit and on admission in each treatment period.

A urine drug abuse test will be performed at the screening visit and on admission in each treatment period.

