11.2 Ethical conduct of the study

The study will be conducted in accordance with the Declaration of Helsinki guiding physicians in biomedical research involving human subjects.

The study shall not be initiated before favourable opinion from the EC and approval from the CA has been obtained for the protocol.

The study will be conducted in compliance with the protocol, GCP (ICH/135/95) and applicable regulatory requirements. A substantial amendment shall not be implemented until the protocol amendment has received a favourable opinion from the EC and approval from the CA. Only in case of the need to eliminate an immediate hazard(s) to study subjects, the investigator may implement deviation from the protocol without prior favourable opinion from the EC and approval from the CA for the protocol amendment.

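### Exclusion criterion 8 requires raised creatinine and a raised transaminase together, so the only numeric liver limit at entry does not work on its own

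*Protocol*

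**What the plan says.** Item 8 of the exclusion criteria (Protocol 4.3) reads: "Creatinine > 1.5 x upper limit of normal (ULN) and alanine aminotransferase or aspartate aminotransferase >1.25 x ULN at screening". The opening line of 4.3 makes any single numbered item sufficient for exclusion. It does not separate the conditions inside one item.

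Two other items in 4.3 could catch a raised liver test. Item 1 covers clinically significant disease, including hepatic and renal disease. Item 3 covers a clinically significant abnormal laboratory value or ECG "that in the opinion of the investigator could interfere with the interpretation of study results or cause a health risk for the subject"; its only numeric examples are QTcF and QRS.

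Section 6.1.1 ties entry to the list: "A subject will be entered into the study if all of the inclusion criteria and none of the exclusion criteria are met". Section 1.3 states that "the events of increase in liver tests, cardiac arrhythmias and gastrointestinal irritation are considered as important potential risks for ODM-104" and describes the purpose of screening: "Samples for laboratory tests and ECG monitoring are applied to exclude subjects with abnormalities from entering the study".

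On treatment, section 4.5 lists among the reasons for stopping: "Increase in alanine aminotransferase, aspartate aminotransferase or alkaline phosphatase to >3 x ULN". Section 6.4.5 sets the schedule: "The following selected laboratory tests will be performed on days 1 and 7 in each treatment period, before the first dose". The selected tests include ALT and AST.

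**The concern.** The protocol gives a numeric transaminase cut-off, but the wording makes it depend on raised creatinine. A healthy man with ALT or AST above 1.25 x ULN and creatinine within its limit does not meet item 8, whatever the size of the elevation. The creatinine limit is disabled in the same way when the transaminases are within theirs.

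This is an operative rule that the site is told to apply, and it concerns a named risk of the study drug in volunteers who get no direct health benefit from dosing. Section 1.3 also reports isolated mild transaminase increases in earlier ODM-104 studies. As worded, whether such a man is dosed is decided case by case. There is also a record-keeping problem. Section 4.4 requires the criterion that caused an exclusion to be recorded, so a site that screens him out under item 8 would cite a criterion he does not literally meet. Finally, screening is the baseline for laboratory changes (Protocol 8.4.5.3, SAP 7.2.3 and 8.5.2), so raised entry values would make a liver signal harder to read.

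**Working it through.** There is no figure in the plan to reproduce. The check is logical, with a search of both documents for any other numeric liver limit at entry.

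**Inputs** (Protocol 4.3, item 8). Three yes/no flags at screening:
- Cr: creatinine >1.5 x ULN
- ALT: ALT >1.25 x ULN
- AST: AST >1.25 x ULN

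**Rules compared**
- Separate limits (probable intention): Cr OR ALT OR AST
- Reading 1 (natural literal reading): Cr AND (ALT OR AST)
- Reading 2 (strained): (Cr AND ALT) OR AST

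Reading 1 is the natural one because ALT has no limit of its own unless it shares the 1.25 x ULN attached to AST. Reading 2 is shown only to test whether another grouping rescues the criterion.

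Three flags give 2 x 2 x 2 = 8 profiles, of which 7 have at least one flag raised:

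| Cr | ALT | AST | Separate limits | Reading 1 | Reading 2 |
|---|---|---|---|---|---|
| 1 | 0 | 0 | excluded | missed | missed |
| 0 | 1 | 0 | excluded | missed | missed |
| 0 | 0 | 1 | excluded | missed | excluded |
| 0 | 1 | 1 | excluded | missed | excluded |
| 1 | 1 | 0 | excluded | excluded | excluded |
| 1 | 0 | 1 | excluded | excluded | excluded |
| 1 | 1 | 1 | excluded | excluded | excluded |
| **Excluded** | | | **7 of 7** | **3 of 7** | **5 of 7** |

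Reading 1 misses 7 - 3 = 4 profiles: creatinine alone, ALT alone, AST alone, and both transaminases with creatinine within its limit. Reading 2 misses 7 - 5 = 2: creatinine alone and ALT alone. Those two are missed either way.

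**Other numeric liver limits.** Items 1 and 3 carry none. The Protocol synopsis and the SAP give none for entry. The only other one is the stopping threshold of 3 x ULN in section 4.5, which stands at 3.0 / 1.25 = 2.4 times the entry limit. A subject entering just above 1.25 x ULN would need a further rise of about 140% to reach it; one entering higher would need less.

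**Timing.** After the day 1 pre-dose sample, the next scheduled liver test in a period is pre-dose on day 7, after six days of carbidopa with or without ODM-104.

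**The case against.** The strongest reply is that this is a drafting slip with an obvious meaning. Requiring renal and hepatic abnormality together makes little clinical sense, item 7 places systolic and diastolic limits under one number evidently as alternatives, and section 1.3 states the purpose of screening. A sensible investigator would probably read item 8 as separate limits, and nothing in the documents shows that the site would do otherwise.

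Protection is also far from absent. Items 1 and 3 apply without any creatinine condition, and inclusion criterion 2 requires good general health. Subjects are housed throughout dosing, and liver tests are repeated in every period and at the end of the study. Section 4.5 requires treatment to stop whenever the investigator or sponsor finds it medically necessary, not only at 3 x ULN.

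Most of this stands, and it limits the consequence. The profile counts are not risks, and Reading 2 is not a serious candidate. The 2.4-fold ratio describes the distance between two protocol limits and would be the same after the fix. Likewise, the absence of a numeric on-treatment rule between 1.25 and 3 x ULN does not come from item 8 and would remain.

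What does not stand is the step from an obvious intention to leaving the text alone. The same list expresses alternatives correctly elsewhere: 'or' in item 6, separate bullets in item 7, 'and/or' in items 13 and 14. Every entry safeguard named above rests on judgement, whereas the sponsor chose to state a number.

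**Conclusion.** The concern holds. As written, item 8 excludes 3 of the 7 profiles that separate limits would exclude, and the transaminase limit has no effect unless creatinine is also raised. Neither document supplies another numeric liver limit for entry, so exclusion of an isolated elevation rests on clinical judgement. The loss is of an objective entry rule for a named ODM-104 risk, not of all protection.

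This rests on applying the criterion literally, as section 6.1.1 directs. If the site reads it as separate limits, no one is wrongly admitted, but the text still needs to agree with that practice. How many volunteers would fall in the gap cannot be estimated, because the documents give no distribution of screening values. Sample size, significance level and the primary comparison are untouched. It should be corrected.

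**What to change.** Reword item 8 as: *Creatinine >1.5 x ULN, or ALT >1.25 x ULN, or AST >1.25 x ULN at screening.* Alternatively, split it into 8a (creatinine) and 8b (ALT or AST). Keep the sponsor's cut-offs and leave items 1 and 3 as they are, so that judgement supplements the numeric rule.

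The cost is a short amendment to one criterion and possibly a few more screen failures. If the change is classed as substantial, section 11.2 applies: "A substantial amendment shall not be implemented until the protocol amendment has received a favourable opinion from the EC and approval from the CA". No change to the SAP is needed.

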4.4 Information collected on screening failures

For subjects screened but not included in the study, the following electronic case report forms (eCRFs) will be completed: date of the screening visit, IC, demography (sex, year of birth, age and racial group), criteria causing the exclusion, decision of entry, adverse events (AEs) related to study assessments and SAEs.

4.5 Removal of subjects from treatment or assessment

Study subjects are free to discontinue the study at any time without providing a reason. However, the investigator should try to identify the reason and document it on the eCRF.

A subject must discontinue the study treatment if the investigator or the sponsor considers the discontinuation to be medically necessary or in the best interest of the subject.

A subject must discontinue the study treatment for example for the following reasons:

- Personal reason
- AE requiring discontinuation of the study treatment, as judged by the investigator:
 - Intolerable dopaminergic AEs such as prolonged moderate or severe vomiting with massive fluid loss and consequent circulatory disorders
 - Intolerable gastrointestinal AEs such as prolonged moderate or severe diarrhoea with massive fluid loss and consequent circulatory disorders
 - Abnormal 12-lead ECG finding of clinical relevance:
 - increase in QTc of >60 ms from baseline
 - increase in QRS of >25% from baseline

- 2nd or 3rd degree atrioventricular block
- sustained (>30 s) cardiac arrhythmias (supraventricular or ventricular tachycardia, atrial fibrillation and/or flutter)
- any symptomatic arrhythmia (except isolated extrasystoles)
- Increase in alanine aminotransferase, aspartate aminotransferase or alkaline phosphatase to >3 x ULN
- Other AE (e.g. fainting or profound weakness) requiring discontinuation of the study treatment
- Lost to follow-up
- Protocol deviation that could affect the outcome of the study, as judged by the investigator
- Other reason (e.g. impossibility to obtain blood samples)

Irrespective of the reason for discontinuation, the subject should be invited to end-of-study assessments as soon as possible. As long as the subject consents, all relevant assessments, at least those of safety, should be performed, preferably according to the schedule for the end-of-study assessments.

The study monitor should be notified about premature discontinuations within 24 h in the event of discontinuation due to an SAE (see section 6.4.1.3) or within 7 days in the event of discontinuation due to another reason.

The sponsor will decide if study subjects who prematurely discontinue will be replaced. Discontinued study subjects are not allowed to re-enter the study.

5. STUDY TREATMENTS

Manufacturing, packaging, and labelling of the study treatments will comply with good manufacturing practice (GMP) regulations (Annex 13 of EU guide to GMP).

5.1 Investigational medicinal products

5.1.1 Test products

5.1.1.1 ODM-104 capsules

ODM-104 capsules in 50 mg and 100 mg strengths are provided in size 0 hard gelatine capsules for oral administration. The colour of the capsules is Swedish orange. ODM-104 capsules are manufactured by Patheon UK Limited, the United Kingdom.

The capsules are stored below 30°C

5.1.1.2 Levodopa 50 mg, 100 mg and 150 mg capsules (Levodopa 50 mg, 100 mg and 150 mg A CAP)

Levodopa MR capsules in 50 mg, 100 mg and 150 mg strengths will be provided in size 0 hard gelatin capsules for oral administration. The colour of the capsules is white. Levodopa capsules are manufactured by Glatt GmbH, Germany.

The capsules are stored below 30°C.

